### **2.3 Additional Objectives**

- To assess OS
- To compare the CR rate in patients who relapsed after frontline therapy with the CR rate in patients who were refractory to frontline therapy
- To assess the feasibility of stem cell mobilization and collection after treatment with brentuximab vedotin in combination with nivolumab
- To assess PFS
- To assess pharmacokinetics (PK) and incidence of antitherapeutic antibodies (ATA) against each study drug given in combination
- To assess tumor amplification and expression of PD-L1/L2 and relationship to response
- To assess tumor microenvironment and peripheral immune status
- To compare safety and efficacy of treatment with staggered versus same-day dosing schemes
- To compare biomarker data obtained with staggered versus same-day dosing schemes
- To assess efficacy in patients who previously received brentuximab vedotin

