### Study Population

Key eligibility criteria include adult (aged  $\geq 18$  years) patients with relapsed or refractory HL following failure of standard frontline chemotherapy for the treatment of classical HL. Patients must have an Eastern Cooperative Oncology Group (ECOG) performance status of 0 or 1 and qualifying baseline laboratory data. Patients are excluded if they were previously treated with immuno-oncology agents or previously received an autologous or allogeneic stem cell transplant. Patients with documented history of a cerebral vascular event, history of another invasive malignancy that has not been in remission for at least 3 years, or history of progressive multifocal leukoencephalopathy (PML) are also excluded. There will be 3 parts in this study; each part will be enrolled sequentially. For Parts 1 and 2, patients previously treated with brentuximab vedotin are

excluded; for Part 3, patients who were treated with brentuximab vedotin are eligible under the following conditions: 1) patient's HL was not primary refractory to a brentuximab vedotin-containing regimen in first line, i.e., patient achieved a CR to a brentuximab vedotin-containing regimen and did not progress within 3 months of the last dose of brentuximab vedotin; and 2) brentuximab vedotin was not discontinued due to unacceptable toxicity.

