### **3.2.2 Method of Assigning Patients to Treatment Groups**

In this open-label study, each part of the trial will enroll sequentially. Enrollment and treatment in Part 1 will be completed before enrollment begins in Part 2, which will evaluate a staggered dosing schedule of brentuximab vedotin and nivolumab in Cycle 1 followed by same-day dosing of both drugs in Cycles 2 through 4.

After enrollment in Part 2 is complete, approximately 30 patients will be enrolled in Part 3 to evaluate same-day dosing of brentuximab vedotin and nivolumab in all treatment cycles.

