#### **4.2 Exclusion Criteria**

1. Patient has received prior salvage therapy, including salvage radiotherapy, for relapsed or refractory classical HL
2. Chemotherapy or biologics therapy that is not completed 4 weeks prior to the first dose of study drug(s), unless documented progression of underlying disease on treatment
3. Prior radiation therapy within 3 weeks, or chest radiation  $\leq 12$  weeks prior to first dose of the study drug(s)
4. For patients in Parts 1 and 2, previous treatment with brentuximab vedotin; for Part 3, patients with HL that is refractory to a brentuximab vedotin-containing regimen in first line, or patients who discontinue brentuximab vedotin due to unacceptable toxicity are ineligible. Refractory disease is defined as never achieving a CR to frontline therapy or having a CR but then progressing within 3 months of completing frontline therapy
5. Has received any prior immuno-oncology therapy (e.g., therapies affecting the PD-1, CTLA4, or CD137 pathways)
6. Previously received an allogeneic and/or autologous stem cell transplant for HL
7. Current therapy with other systemic antineoplastic or investigational agents
8. Systemic treatment with either corticosteroids ( $>10$  mg daily prednisone equivalent) or other immunosuppressive medications within 14 days of enrollment
  - Inhaled or topical steroids and adrenal replacement steroid doses  $>10$  mg daily prednisone equivalent, are permitted in the absence of active autoimmune disease
9. History of another primary invasive malignancy that has not been in remission for at least 3 years
10. History of progressive multifocal leukoencephalopathy (PML)

11. Known cerebral/meningeal disease related to the underlying malignancy
12. Pre-existing neuropathy of Grade 2 or greater
13. Any active Grade 3 or higher (per the National Cancer Institute's Common Terminology Criteria for Adverse Events [NCI CTCAE], Version 4.03) viral, bacterial, or fungal infection within 2 weeks prior to the first dose of brentuximab vedotin; routine antimicrobial prophylaxis is permitted
14. Females who are pregnant or breastfeeding
15. Known hypersensitivity to any excipient contained in the drug formulation of brentuximab vedotin or nivolumab
16. Positive for hepatitis B by surface antigen expression, or any other positive test for hepatitis B virus indicating acute or chronic infection

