### **6.4 End of Treatment Visit (30 to 37 days after last dose of study drug except where noted)**

EOT visits should occur 30 to 37 days after the last dose of study drug(s) unless delayed due to an AE. However, EOT evaluations must be performed before initiation of a new therapy, other than mobilization of stem cells for ASCT. If EOT evaluations are completed before 30 days after the last study treatment, the patient will be contacted 30 to 37 days following the last treatment to assess for adverse events. The following activities will be conducted at EOT:

- B symptom assessment
- Performance status

- Physical examination
- Inflammatory condition review (only for those patients with certain inflammatory conditions of interest at Screening/Baseline)
- Serum chemistry panel (includes TSH, free T3, and free T4; see Section 7.6.2)
- CBC with differential (see Section 7.6.2)
- ANA
- Blood samples for PK and ATA assessments
- Blood samples for biomarker assessments and flow cytometry
- Tumor biopsy; optional at progression of disease or if evidence of residual disease is suspected (Note: Strongly recommended to confirm that radiological evidence of progression is correlated with active HL; when possible, excisional biopsies should be performed)
- For patients in Parts 1 and 2: PET and dedicated CT of chest, neck, abdomen, and pelvis; PET and CT scans to be performed 23 to 37 days after last dose of study drug (as described in Section 7.2.1)
- For patients in Part 3: PET and dedicated CT of chest, neck, abdomen, and pelvis; PET and CT scans to be performed 15 to 30 days after last dose of study drug (as described in Section 7.2.2)
- Bone marrow biopsy (for patients planning to proceed to ASCT)

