##### **9.3.1.1 Randomization and Blinding**

No randomization will be carried out and no blinding will be enforced as this is an open-label trial.

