7.5 Efficacy Analyses

The test of the primary efficacy endpoint of CR rate will be carried out using the All Enrolled Patients analysis set. Other efficacy analyses will be carried out using the All Enrolled Patients analysis set, and may also be presented using the Efficacy Evaluable analysis set or the All Treated Patients analysis set.

Unless otherwise specified, efficacy analyses will be presented by dose regimen and overall.

Additional exploratory subgroup analyses may be carried out as well.

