7.5.1 Primary Efficacy Endpoints

7.5.1.1 Complete Remission (CR) Rate

CR rate is defined as the proportion of patients with best response of CR prior to ASCT or initiation of subsequent antitumor treatment not specified in the protocol. Response is by investigator assessment according to the Lugano Classification Revised Staging System for malignant lymphoma (Cheson 2014). For Part 3, the response assessment will also incorporate the Lymphoma Response to Immunomodulatory Therapy Criteria (LYRIC) (Cheson 2016). Patients whose response to treatment cannot be adequately assessed according to the specified criteria will be classified as non-responders for the purpose of calculating CR rate.

The primary efficacy hypotheses can be expressed as follows:

 H_0 : CR Rate for brentuximab vedotin + nivolumab is $\leq 30\%$

H_A: CR Rate for brentuximab vedotin + nivolumab is >30%

The CR rate at EOT will be calculated using the All Enrolled Patients analysis set and will include all patients in this analysis set who were enrolled at the dose regimen chosen for Part 2. The test of the primary hypothesis will be carried out using a one-sided exact binomial test at level $\alpha = 0.05$, thus the null will be rejected in favor of the alternative if p <0.05 is observed. CR rate and its two-sided 90% (to correspond with the level of the test) exact binomial confidence interval will be calculated (Clopper 1934). Additionally, the two-sided 95% exact binomial confidence interval will be presented as a descriptive summary.

CR rate will also be summarized separately for patients enrolled under dose regimens other than that chosen for part 2 of the study. Overall summaries of CR rate may be presented as well. These summaries will be considered exploratory in nature.

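### The SAP omits the protocol's staggered versus same-day comparison, and its default split by dose regimen would set brentuximab-naive patients against a Part 3 group that may include exposed ones

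*Protocol*

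**What the plan says.** Protocol 2.3 and the Synopsis include the additional objective "To compare safety and efficacy of treatment with staggered versus same-day dosing schemes". The same list has two related objectives: a biomarker comparison between the schedules, and efficacy in patients who had brentuximab vedotin before. SAP 2.3 carries none of the three. The SAP does not predate Part 3: its sections 4, 6.2 and 7.5.1.1 cover Part 3 dosing, sample size and response criteria. Its section 9.1 on changes does not mention the omission.

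For efficacy, SAP 7.5 gives a default: "efficacy analyses will be presented by dose regimen and overall". No method for comparing the schedules is stated in either document. Protocol 9.1 and SAP 6.2 specify no formal test for Part 3.

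The two groups differ as follows.

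| Feature | Parts 1 and 2 (staggered) | Part 3 (same-day) | Protocol section |
|---|---|---|---|
| Prior brentuximab vedotin | Excluded | Allowed under conditions, no quota | 4.2; Synopsis, Study Population |
| EOT CT/PET, days after last dose | 23–37 | 15–30 | 6.4 |
| Response criteria | Lugano | Lugano plus LYRIC | 7.2, 9.2.1.1 |
| Apparent progression at Cycle 2 | Study treatment ends | May continue if the response is indeterminate | 3.1.1, 3.1.2 |
| Premedication | Corticosteroid and antihistamine from Cycle 2 | Antihistamines from Cycle 1, corticosteroid only after a reaction | 5.4.1, 5.4.2 |

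On eligibility, exclusion criterion 4 reads "For patients in Parts 1 and 2, previous treatment with brentuximab vedotin", whereas the Synopsis says "for Part 3, patients who were treated with brentuximab vedotin are eligible under the following conditions". On scans, Part 3 has "PET and CT scans to be performed 15 to 30 days after last dose of study drug". On allocation, Protocol 3.2.2 says "In this open-label study, each part of the trial will enroll sequentially" and Protocol 9.3.1.1 says "No randomization will be carried out and no blinding will be enforced as this is an open-label trial".

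**The concern.** A stated objective has no planned analysis. Under SAP 6.1, anything not described in the plan is reported as exploratory, either post hoc or as a change. The only ready-made contrast is therefore the split by regimen. That split changes the patient population along with the schedule, so a lower CR rate in Part 3 could be put down to same-day dosing when it came from pretreated patients. A real schedule effect could also be masked.

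Prior exposure is the difference that the analysis can most easily separate, because SAP 7.2 already tabulates prior therapies and the response to them. Yet it is not among the example subgroups in SAP 6.8, and SAP 6.9 names no covariate.

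**Working it through.** **1. The plan's own figures.** The exact (Clopper-Pearson) 95% CI for 19/30 is 43.9% to 80.1%; Protocol 9.1 gives 44% to 80%, so it reproduces. For the interim result in Protocol 3.2.1, 18/29 = 62%, the exact CI is 42.3% to 79.3%, as stated.

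**2. Precision of the schedule contrast.** Inputs: about 55 patients in Parts 1 and 2 and 30 in Part 3 (Protocol 9.1), with a CR rate of 62% in both groups (the interim figure, used as a planning value).

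Half-width = 1.96 × √[0.62 × 0.38 × (1/55 + 1/n₃)]

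- n₃ = 30: 1.96 × √(0.2356 × 0.0515) = 0.216, about 22 points
- n₃ = 27: 1.96 × √(0.2356 × 0.0552) = 0.224, about 22 points
- n₃ = 15: 1.96 × √(0.2356 × 0.0848) = 0.277, about 28 points

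For scale only, since no test is planned: with 55 versus 30 patients and a two-sided 5% level, power is about 42% for 62% versus 42%, and about 82% for 62% versus 30%.

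**3. What prior exposure could do to the CR rate.** Suppose the schedule has no effect and naive patients reach 62% on either schedule. With a fraction f of Part 3 exposed and CR rate p in those patients:

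Shift in Part 3 CR = f × (p − 0.62)

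| f | p = 30% | p = 45% | p = 62% |
|---|---|---|---|
| 10% | −3.2 points | −1.7 | 0 |
| 20% | −6.4 | −3.4 | 0 |
| 30% | −9.6 | −5.1 | 0 |
| 50% | −16.0 | −8.5 | 0 |

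The documents give neither f nor p for the combination. The 30% is the CR rate on single-agent brentuximab retreatment (Protocol 1.3.1) and serves only as a low anchor. The 45% is an arbitrary midpoint, and 62% represents no effect of exposure.

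**4. Scan timing.** The window midpoints are (23 + 37)/2 = 30 and (15 + 30)/2 = 22.5 days, which is 7.5 days apart; the windows overlap on days 23 to 30. Cycle 2 imaging is CT only in both groups, and SAP 6.4 requires CT plus PET to determine response. The EOT scan is thus the first scheduled on-study PET and largely settles CR.

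**5. LYRIC.** A Deauville score of 3 or less defines complete metabolic response in both groups (Protocol 7.2.1, 7.2.2). LYRIC can reach CR only indirectly, when a Part 3 patient continues after an indeterminate response and later responds. Its direct effects are on the date of PD, and so on PFS and duration of response. The PFS and duration rules in SAP 7.5.2 and 7.5.3 do not say how an indeterminate response is treated.

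**The case against.** The strongest reply is that little rests on this. The objective is an additional one with no hypothesis test or decision rule. SAP 7.5.1.1 already calls CR summaries for regimens other than that of Part 2 exploratory. The protocol is open about sequential, non-randomized enrollment. The SAP also permits further subgroups (6.8) and covariate-adjusted analyses (6.9). All of this stands, and it limits the point to interpretation. But permission is not a plan: neither the objective nor prior brentuximab exposure is named.

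A reader might infer that Part 3 CR will be biased downward by 3 to 16 points. The documents do not support that. The 30% comes from brentuximab alone, whereas Part 3 gives the combination. Exposed patients must have had a CR to their earlier brentuximab regimen without progressing within 3 months (Synopsis), which may favor them. Protocol 1.3.2 also reports no significant difference in ORR with nivolumab in 18 patients who had failed brentuximab. The bias could be zero or reversed, and every shift in the table is smaller than the 22-point half-width.

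A reader might also infer that CR is scored by a different standard in Part 3. It is not; the metabolic threshold is the same.

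Finally, a reader might infer that restricting Part 3 to naive patients would isolate the schedule. It would not: calendar time, scan timing and premedication still differ.

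**Conclusion.** The gap is real and worth closing. The SAP drops a protocol objective, and its default summary would mix schedule with prior brentuximab exposure. The bias in CR has unknown size and direction. The range from 0 to a 16-point deficit shown above rests on an assumed exposed share of 10% to 50% and an assumed CR rate of 30% to 62% in exposed patients; an advantage for Part 3 cannot be excluded. LYRIC matters mainly for PD, PFS, duration of response and continued treatment. Premedication matters for infusion-reaction rates.

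The primary test is untouched, because it uses patients on the regimen chosen for Part 2. No reanalysis can turn this sequential, non-randomized contrast into a clean estimate of the schedule effect. Removing the known population difference is nevertheless a better default than the split by regimen.

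**What to change.** In the SAP:

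1. Restore the objective, label the comparison descriptive and non-randomized, and state that it contrasts schedules. The regimen table in SAP 7.4 distinguishes mg/kg levels only.
2. Present the CR difference with a 95% CI for Parts 1 and 2 versus brentuximab-naive Part 3 patients, beside the result for all of Part 3.
3. Report brentuximab-exposed Part 3 patients separately, as the protocol's own objective implies.
4. Add a sensitivity analysis of PFS and duration of response in which an indeterminate response that meets Lugano PD counts as PD on that date. State how a later CR in such a patient is counted.
5. Tabulate days from last dose to EOT scan by part. Do not restrict to the shared window of days 23 to 30: scan day arises after treatment, and EOT visits may be delayed for an adverse event (Protocol 6.4), so restriction could add selection bias.
6. Note that infusion-reaction rates are confounded by premedication.

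The cost is SAP text, a few tables and some precision: a half-width of about 22 points if nearly all Part 3 patients are naive, rising to about 28 with 15 naive patients. Item 4 may need more work, because the documents do not say that a Lugano category is recorded alongside an indeterminate response. The Part 3 images supplied to the sponsor (Protocol 7.2.2) could serve for those cases. Dosing and patient management do not change.

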## **2.4 Endpoints**

### **2.4.1 Primary Endpoints**

- Type, incidence, severity, seriousness, and relatedness of AEs and laboratory abnormalities
- CR rate following the completion of study treatment

### **2.4.2 Secondary Endpoints**

- ORR

- Duration of CR and OR
- PFS post-ASCT

#### **2.4.3 Additional Endpoints**

- OS
- PFS
- Selected PK, ATA, and biomarker endpoints

### 3 INVESTIGATIONAL PLAN

[figure not shown]
#### 3.1 Summary of Study Design

This is a phase 1/2, open-label, multicenter study designed to evaluate the safety and antitumor activity of brentuximab vedotin treatment combined with nivolumab. The study will be conducted in 3 parts.

##### 3.1.1 Study Design Parts 1 and 2

Patients in Parts 1 and 2 will be treated for up to four 21-day cycles. The first dose of brentuximab vedotin will be given on Cycle 1 Day 1. The first dose of nivolumab will be given on Cycle 1 Day 8. For Cycle 2 and all subsequent cycles, both brentuximab vedotin and nivolumab will be administered on Day 1. Nivolumab will be administered at least 30 minutes after infusion of brentuximab vedotin is complete (Figure 1).

**Figure 1: Study design: Staggered dosing in Cycle 1 (Parts 1 and 2)**

[figure not shown]
- a Each cycle consists of 21-days. At Cycle 1, 1.8 mg/kg brentuximab vedotin is administered on Day 1, followed by 3 mg/kg nivolumab on Day 8. At subsequent cycles, 1.8 mg/kg brentuximab vedotin and 3 mg/kg nivolumab are both administered on Day 1.
- b Response assessment performed at Screening/Baseline, between Days 15–21 at Cycle 2, and at EOT. CT only at Cycle 2 to assess for progressive disease. CT/PET at Screening/Baseline, EOT (23–37 days post last dose of study drug), and during long-term follow-up until a patient has achieved CmR by PET assessment; once a patient has achieved CmR by PET assessment, responses will be followed by CT scans of diagnostic quality only.
- c All patients who receive at least one dose of brentuximab vedotin will have long-term follow-up assessments at the following time points post-ASCT (or for patients who do not undergo ASCT, post-EOT): 100 days and then 6, 9, 12, 18, 24, 30, and 36 months, and then per institutional standard thereafter. A final safety visit will be performed 100 days after the last dose of nivolumab and after the EOT to assess for potential immune-mediated adverse events. Patients will be followed at this schedule until withdrawal of consent, death, or study closure, whichever occurs first.

Patients in Parts 1 and 2 with radiographic evidence of progressive disease (PD) at the Cycle 2 response assessment are not eligible for further treatment on the study. All other patients in Parts 1 and 2 are eligible to continue treatment on study through Cycle 4. After completion of the end-of-treatment (EOT) response assessments, patients are eligible to undergo ASCT. It is recommended that hematopoietic stem cells (HSC) be mobilized and collected after Cycle 4. However, stem cell collection may occur in prior cycles after discussion with the medical monitor. If patients have an unacceptable toxicity that is attributable to only one agent, as determined by the investigator, they will be eligible to continue on the treatment protocol through Cycle 4 with the tolerated drug as a single agent.

### 3.1.2 Study Design Part 3

In Part 3, patients will be treated for up to four 21-day cycles. Both brentuximab vedotin and nivolumab will be administered on Day 1 of all cycles (Figure 2); nivolumab will be administered at least 30 minutes after infusion of brentuximab vedotin is complete.

**Figure 2: Study design: Same-day dosing in all treatment cycles (Part 3)**

- a On Day 1 of each 21-day cycle, both brentuximab vedotin 1.8 mg/kg and nivolumab 3 mg/kg will be administered.
- b Response assessment performed at Screening/Baseline, between Days 15-21 at Cycle 2, and at EOT. CT only at Cycle 2 to assess for progressive disease. CT/PET at Screening/Baseline, at EOT (15-30 days post last dose of study drug) and during long-term follow-up until a patient has achieved CmR by PET assessment; once a patient has achieved CmR by PET assessment, responses will be followed by CT scans of diagnostic quality only.
- c All patients who receive at least one dose of either study drug will have long-term follow-up assessments at the following time points post-ASCT (or post-EOT for patients who do not undergo ASCT): 100 days and then 6, 9, 12, 18, 24, 30, and 36 months, and then per institutional standard thereafter. A final safety visit will be performed 100 days after the last dose of nivolumab and after the EOT to assess for potential immune-mediated adverse events. Patients will be followed at this schedule until withdrawal of consent, death, or study closure, whichever occurs first.

Patients in Part 3 with confirmed, unequivocal PD at Cycle 2 are not eligible for further treatment and will proceed to the EOT visit. Patients with stable disease (SD) or better at the Cycle 2 response assessment may continue on treatment through Cycle 4. Patients with an indeterminate response (IR), as defined by the Lymphoma Response to Immunomodulatory Therapy Criteria (LYRIC; [Appendix D](#)) ([Cheson 2016](#)), also may continue on treatment through Cycle 4. After completion of the EOT response assessment, patients are eligible to undergo ASCT. It is recommended that HSC be mobilized and collected after Cycle 4. However, stem cell collection may occur in prior cycles after discussion with the medical monitor. If patients have an unacceptable toxicity that is attributable to only one agent, as determined by the investigator, they will be eligible to continue on the treatment protocol through Cycle 4 with the tolerated drug as a single agent.

